### **4.2.2 Secondary endpoints**

#### **4.2.2.1 Maternal endpoints**

- Incidence of major hypoglycaemia during pregnancy
- Proportion of pregnancies where the woman experiences at least one major hypoglycaemic event during pregnancy
- Proportion of pregnancies complicated by pre-eclampsia during pregnancy
- HbA1c level assessed as close as possible to conception, end of first trimester, end of second trimester, and at delivery.

#### 4.2.2.2 Pregnancy outcome endpoints

- Proportion of pregnancies resulting in perinatal death assessed at 1 week after delivery
- Proportion of pregnancies resulting in neonatal death assessed at 4 weeks after delivery
- Proportion of pregnancies resulting in live birth with major congenital malformations and by organ assessed at delivery
- Proportion of pregnancies resulting in live birth with minor congenital malformations and by organ assessed at delivery
- Proportion of induced abortions due to major congenital malformations and by organ assessed at delivery
- Proportion of pregnancies resulting in spontaneous abortion assessed at pregnancy termination
- Proportion of pregnancies resulting in live birth with foetal macrosomia assessed at delivery
- Proportion of pregnancies resulting in live born infants with birth weight > 90th percentile for gestational age and sex (local reference) assessed at delivery
- Proportion of pregnancies resulting in pre-term delivery assessed at delivery

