## 2 Flow chart

Flow chart of visits and standard routine procedures.

Visit	Baseline visit	Standard routine visits	Delivery visit	Follow-up of the infant(s)	Follow-up of the infant(s)
Time of visit	≤ 16 weeks pregnant	Any time during pregnancy	Delivery	1 month after delivery	1 year after delivery
Visit window				+ 1 month	+ 4 months
Informed consent	x				
Incl. /excl. criteria	x				
Demographics	x				
Obstetric history	x				
Maternal medical history	x				
Maternal diabetes history	x				
Current antidiabetic treatment	x	x	x		
Concomitant illness	x				
Concomitant medication	x	x	x		
Height 	x		x	x	x
Weight 	x	x	x	x	x
Vital signs	x	x			
Current pregnancy information	x				
HbA 1c	x 	x	x		
Major hypoglycaemia		x	x		

Pre-eclampsia		x	x		
ADRs and SAEs 		x	x	x	x
Delivery and complications			x		
Pregnancy outcome			x		
Neonatal assessments			x		
Foetal assessments 			x		
Neonatal death				x	
Congenital malformations not detected at delivery				x	
Lactation				x	x
Diabetes					x
Changes of major congenital malformations					x

1. Height and weight of the mother during pregnancy and of the infant(s) at delivery, 1 month and 1 year follow-up
2. HbA1c measured ≤ 16 weeks prior to baseline visit is acceptable as baseline visit data (see section [8.1.1](#))
3. Relevant ADR's and SAE's according to protocol section [9](#)
4. Foetal assessments in case of early termination of pregnancy, perinatal and neonatal death
5. Preferably data from one standard routine visit per month should be entered into the eCRF irrespectively of the number of visits performed

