##### *Pregnancy outcome*

Comparison of pregnancy outcomes in women treated with Levemir® to those treated with other basal insulin regimens with respect to:

- Foetal macrosomia
- Large-for gestational age
- Pre-term delivery
- Spontaneous abortion
- Induced abortion due to major congenital malformations (by organ)
- Perinatal death
- Neonatal death
- Live birth with major congenital malformations(by organ)
- Live birth with minor congenital malformations(by organ)

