## **4.2 Endpoints**

### **4.2.1 Primary endpoints**

Comparison of the proportion of pregnancies in pregnant women who have completed 22 weeks of pregnancy and treated with Levemir® to pregnant women who have completed 22 weeks of pregnancy and treated with other basal insulin regimens resulting in none of the following events:

- Major congenital malformations
- Perinatal death
- Neonatal death

Assessed at up to 4 weeks after delivery.

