### 6.1 Number of patients to be studied

Estimated number of patients to be included during the recruitment period: minimum: 2,037

Recruitment will close once it is secured that 611 patients treated with Levemir® are eligible for the primary analysis.

Based on sample size calculations (Section 14) the number of pregnancies needed for the primary endpoint calculations is 1,222 pregnancies with information on the primary endpoint pregnancy outcomes:

- perinatal death
- neonatal death
- liveborn infant with 1 month follow up (irrespective if there is a malformation or not)

Liveborn infants will be followed up until 1 year with the aim of collecting data for the secondary endpoints.

It is expected that approximately 60% of the included pregnancies will be fulfilling the criteria for primary endpoint calculations, as 40 % are assumed to be excluded or used for secondary endpoints. These 40% of subjects are assumed to consist of subjects who experience one or more of the following: abortion (spontaneous or induced), change in basal insulin treatment, treatment with other antidiabetic treatment regimens, or lost to follow-up.

Therefore, it is calculated that a minimum of  $(1,222/60*100)$  2,037 patients are to be included in the study.

Note that the study plans to include a minimum of 2,037 patients treated with injectable antidiabetic treatment regimens, but that only women treated with Levemir® and other basal insulins will be included in the primary analyses.

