#### **8.1.4 Post partum visit**

The postpartum visit will be a 1 month follow-up data collection of the infants to the women with an allowed visit window of +1 month. The follow-up will be performed as a questionnaire sent to the women and will be followed up with a telephone interview of the women. The date of visit to be entered in the eCRF should be the date where the body measurements were performed. It is not

mandatory to collect the completed questionnaires. The following information will be asked in the questionnaire:

- Height at the age of 1 month (approximately)
- Weight at the age of 1 month (approximately)
- Neonatal death of the infant (y/n)
- Congenital malformations (minor/major) not detected at delivery
- Duration of exclusive lactation and/or duration of partial lactation (section [8.3.13](#))
- If the neonate has experienced any AEs, only ADRs and SAEs should be reported in the eCRF

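### The two live-birth malformation endpoints stop at delivery, while the primary counts major malformations to 4 weeks and later-found ones are collected at 1 month

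*Protocol*

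**What the plan says.** **Secondary endpoints (Section 4.2.2.2).** Two endpoints concern malformations in liveborn infants: "Proportion of pregnancies resulting in live birth with major congenital malformations and by organ assessed at delivery" and "Proportion of pregnancies resulting in live birth with minor congenital malformations and by organ assessed at delivery". A third concerns terminations: "Proportion of induced abortions due to major congenital malformations and by organ assessed at delivery".

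**Matching objective (Section 4.1.2).** It lists "Live birth with major congenital malformations(by organ") and the equivalent for minor malformations, with no time limit.

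**Primary endpoint (Section 4.2.1).** Freedom from major congenital malformation, perinatal death and neonatal death, "Assessed at up to 4 weeks after delivery". Section 6.1 lists what counts as primary-endpoint information, and for survivors this is a "liveborn infant with 1 month follow up (irrespective if there is a malformation or not").

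**Data collection.** The 1-month contact in Section 8.1.4 asks for "Congenital malformations (minor/major) not detected at delivery". The flow chart in Section 2 marks the row "Congenital malformations not detected at delivery" at the same contact. The contact is a questionnaire to the mother followed by a telephone interview, with a window of +1 month.

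The protocol gives no reason for ending the two live-birth endpoints at delivery.

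**The concern.** Section 4.2.2.2 gives the other two components of the composite a time point that fits the primary: perinatal death at 1 week and neonatal death at 4 weeks. Malformation is the component with the largest planning rate (4.5%, against 3% and 0.9%), and it is the only one cut short. The endpoint is also narrower than the objective it serves.

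This is a post-authorisation safety study, and these two endpoints are the only by-organ malformation results for liveborn infants. Followed as written, they leave out cases that the study gathers and, for major malformations, already counts in its primary analysis. A reader who compares the malformation row with the composite would be looking at two different ascertainment periods.

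**Working it through.** **1. The plan's own figure.** Section 14.2 assumes 4.5% major malformation, 3% perinatal death and 0.9% neonatal death, and treats them as independent. (1 − 0.045) × (1 − 0.03) × (1 − 0.009) = 0.955 × 0.97 × 0.991 = 0.918. This reproduces the stated 91.8%. The sample size rests on the primary endpoint, so the present point does not touch it.

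**2. Where a late-found malformation is counted.** Take a liveborn infant, alive at 4 weeks, whose malformation is first found after delivery and by 4 weeks.

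| Endpoint | Major | Minor |
|---|---|---|
| Primary composite (to 4 weeks) | counted | not a component |
| Live birth with malformation (at delivery) | not counted | not counted |
| Perinatal or neonatal death | not applicable | not applicable |
| Induced abortion for malformation | not applicable | not applicable |
| 1-year endpoint (change in a major malformation) | only if it progressed or regressed | not covered |

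The gap follows from the definitions at any late-detected share above zero. Asking the 1-month question at all shows that the protocol allows for such cases.

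**3. Size: illustration only.** The protocol gives no share of malformations first found between delivery and 4 weeks. Call this share s and assume 5% to 30%. Take one infant per pregnancy and 1,222 pregnancies (Section 6.1).

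- *At the planning rate:* 1,222 × 0.045 = 55 major malformations. Omitted cases = 55 × s: 55 × 0.05 = 2.7 (about 3) and 55 × 0.30 = 16.5 (about 16, because 1,222 × 0.045 is just under 55). The at-delivery proportion would read 4.5% × (1 − s), which is 4.275% at s = 5% and 3.15% at s = 30%.
- *At the observed rate:* Section 14.3 reports 97.3% event-free, so 1,222 × (1 − 0.973) = 33 pregnancies with any primary event. If all 33 were malformations, omitted cases = 33 × 0.05 = 1.7 (about 2) to 33 × 0.30 = 9.9 (about 10). Some of the 33 will be deaths without malformation, so this is a ceiling.

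The two lines cannot both be right, since 55 malformations do not fit within 33 pregnancies with any event. The second line is closer to what the study has seen.

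**4. Effect on the comparison.** If the same share s is missed in both groups, each proportion is multiplied by (1 − s). The expected difference is multiplied by (1 − s) too, and the ratio is unchanged. A distorted ratio would need s to differ between the groups, and nothing in the protocol suggests that.

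**5. What the 1-month contact supplies.** Organ is listed for the delivery form (Section 8.3.11) and the foetal/infant death form (Section 8.3.12). The Section 8.1.4 list asks for minor or major only, with neither organ nor date of detection. The visit date to be entered there is the date of the body measurements, so it cannot stand in for the detection date. With the +1 month window, a report can arrive about 2 months after delivery. Congenital anomaly is a seriousness criterion in Section 9, and Section 9.1 requires an AE form and a safety information form for each SAE, with the diagnosis if available. Those forms are the likely source for organ and date.

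**The case against.** The best defence is uniform ascertainment. Findings at delivery come from an examination of the newborn, while the 1-month data come from the mother and will be missing for some infants. A delivery-only endpoint avoids both problems. But the protocol does not give this reason, and its primary endpoint relies on the same 1-month data. Keeping a delivery-only row preserves whatever merit the argument has.

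Four further points stand and limit the finding:

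- **The data are not lost.** A reader might infer that late-found malformations disappear from the study. They do not: major ones count in the primary, and congenital anomalies in offspring are reported as SAEs up to 1 year of age. They are absent from these endpoint definitions.
- **Timing is not the only difference from the composite.** A reader might infer that aligned dates would make the secondaries add up to the primary. They would not. The secondaries cover live births only, whereas the primary covers all pregnancies past 22 completed weeks, and one infant can have a malformation and also die.
- **The induced-abortion endpoint is unaffected.** Section 8.3.12 places these before 22 completed weeks, so the 1-month contact has no bearing on them.
- **These are not key secondary endpoints.** Section 1 does not list the two live-birth malformation endpoints among them.

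**Conclusion.** The finding holds for the two live-birth malformation endpoints, major and minor. Their window ends at delivery, which does not match the malformation component of the primary and is narrower than the stated objective. As defined they under-count. The cause is a time point the protocol itself fixes, so it is not a detail left to the analysis plan.

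The size is not known. The figures of about 3-16 omitted cases of 55, or at most about 2-10 of 33, rest entirely on an assumed late-detected share of 5-30%. The protocol neither supports nor excludes larger shares. A reader might see the glossary's septal defects as evidence of frequent late recognition, but the glossary says nothing about when they are found.

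The protocol also gives no ground for inferring bias in favour of either treatment group. What is shown is an under-count of absolute proportions and, if detection is equal in both groups, a matching shrinkage of the difference. The primary endpoint and the sample size are unaffected. This is a modest defect in a secondary safety output, worth correcting because the correction is cheap.

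**What to change.** In Section 4.2.2.2, define both live-birth endpoints (major and minor, by organ) as malformations detected up to 4 weeks after delivery. State that reports from the 1-month contact are handled by the same rule as in the primary, and say what that rule does with reports arriving late in the +1 month window. Take organ and date of detection from the 1-month form if it holds them, and otherwise from the AE or safety information form. Keep delivery-only counts as a descriptive row, and show infants without a 1-month contact as missing. Leave the induced-abortion endpoint as it is. Add a sentence saying that these endpoints cover live births only and may overlap with the deaths, so they are not expected to sum to the composite.

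**Cost.** No new visit is needed and the sample size does not change. Someone must check that organ and date of detection can be recovered for late cases, and some site queries may follow. The small downside is that late cases rest on maternal report and some infants will have no 1-month contact.

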#### 4.2.2.3 Infant endpoints assessed at 1 year of age

- Height at the age of 1 year
- Weight at the age of 1 year
- Proportion with DM
- Proportion with changes (progression/regression) of major congenital malformations

For pregnancies with multiple foetuses each foetus will be counted individually for the primary endpoint, the other pregnancy outcome endpoints, and the infant endpoints at 1 year of age.

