### **13 Evaluation of patients for analysis**

The analysis set will consist of the pregnancies among patients who are treated with basal insulin and have not changed basal insulin product 4 weeks prior to conception and during pregnancy.

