#### 14.4 Statistical methods

All endpoints will be analysed on the analysis set.

Continuous variables (maternal HbA1c at start of pregnancy, at the end of each trimester, and height and weight of the infant at 1 year) will be summarised with descriptive statistics (number of observations with available values, number of observations with missing values, mean, 95% confidence interval of the mean, standard deviation, minimum, median, maximum), and categorical variables and Apgar score will be displayed in frequency tables (N, %). The mean of the Apgar score will also be computed.

The primary endpoint, proportion of pregnancies resulting in the combined pregnancy outcome will be computed for the Levemir® group, and for the other basal insulin group, the difference between these proportions will be computed along with the 95% confidence interval and the p-value using Fisher's exact test. This simple analysis might be biased if type of basal insulin is confounded with other risk factors for a negative birth outcome, so to take this into account the primary endpoint will also be analysed using logistic regression, see the description below.

This analysis will be performed for all other endpoints which are proportions, both maternal endpoints, pregnancy outcome endpoints, and infants' endpoints at 1 year of age.

In addition, the primary endpoint will be analysed using logistic regression. Both crude and adjusted models will be performed. The model will include treatment group (Levemir®/other basal insulins group), and adjust for potential confounders such as study site, type of DM, race, hypertension, major hypoglycaemic events during pregnancy, folic acid intake, and use of GLP-1 agonists during pregnancy. Furthermore, HbA1c at start of pregnancy, end of first trimester, and end of second trimester, age and BMI of the woman at baseline, duration of DM, blood pressure and previous foetal pregnancy complications will be adjusted for as appropriate. Adjustments will be performed in a stepwise manner, and further specified in the Statistical Analysis Plan. Similar analyses will be performed for all other endpoints which are proportions for maternal endpoints, or proportions for pregnancy outcome endpoints.

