For the infants endpoints at 1 year of age the proportions will also be analysed using logistic regression, the model will include treatment group (Levemir®/other basal insulins group), study site, race, hypertension, major hypoglycaemic events during pregnancy, folic acid intake, and possible use of GLP-1 agonists during pregnancy as factors. Furthermore, HbA1c at start of pregnancy, end of first trimester, and end of second trimester, age and BMI of the woman at baseline, duration of DM, blood pressure and previous foetal pregnancy complications will be included as covariates. The analyses regarding height and weight will also be adjusted for exclusive and/or partial lactation period.

The means of the continuous endpoints (maternal HbA1c at the end of each trimester and, height and weight of the infant at 1 year), will be compared between the Levemir® group and the other basal insulins group using an analysis of covariance (ANCOVA) model.

The incidence of major hypoglycaemia during pregnancy will be computed for both treatment groups.

Additional exploratory hypothesis-generating analyses may also be performed as deemed relevant.

Differences in gestational age at study entry and exact follow-up time will be taken into account in the statistical analysis where relevant.

All statistical analyses will be performed using appropriate statistical software. All statistical tests will be performed as two-sided tests with a significance level of 0.05.

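### The 1-year key secondary endpoint on changes of major malformations has no denominator of its own; on the general analysis set it is confounded with prevalence at birth, and its fixed logistic model has too few events

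*Protocol*

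**What the plan says.** The endpoint is worded "Proportion with changes (progression/regression) of major congenital malformations" in section 4.2.2.3 and appears again among the key secondary endpoints in section 1. Neither place says which infants form the base. Section 4.2.2.3 adds that, in multiple pregnancies, "each foetus will be counted individually for the primary endpoint, the other pregnancy outcome endpoints, and the infant endpoints at 1 year of age".

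The population comes from two general statements. Section 14.4 says "All endpoints will be analysed on the analysis set", and section 13 says "The analysis set will consist of the pregnancies among patients who are treated with basal insulin and have not changed basal insulin product" (from 4 weeks before conception and through pregnancy). That set is not limited to live births or to infants with a malformation.

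Section 14.4 compares proportions by their difference, a 95% confidence interval and Fisher's exact test, and extends this by name to the 1-year infant endpoints. It then adds: "For the infants endpoints at 1 year of age the proportions will also be analysed using logistic regression". The listed terms are treatment group, study site, race, hypertension, major hypoglycaemia, folic acid, GLP-1 agonist use, HbA1c at three time points, maternal age, BMI, diabetes duration, blood pressure and previous foetal complications. Malformation at birth is not among them.

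Prevalence has its own endpoint in section 4.2.2.2: "Proportion of pregnancies resulting in live birth with major congenital malformations and by organ assessed at delivery". Major malformation is also a component of the primary endpoint.

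**The concern.** The endpoint asks how major malformations develop over the first year. An infant without one has nothing that can progress or regress. On the whole set such infants are zeros by construction, and a group difference in prevalence at birth passes straight into a result labelled as change. The same signal could then be reported under the primary endpoint, under malformed live births, and again as a difference in the infants' later course. A true difference in course could also be masked or reversed by a prevalence difference in the other direction.

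A second problem holds on either denominator. The logistic model is written into the protocol for an outcome that will occur in very few infants.

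**Working it through.** **Inputs from the protocol**
- Planning rate of major malformation: 4.5% (section 14.2).
- Observed proportion free of all three primary outcomes: 97.3% (section 14.3).
- Sample size: 1,222, that is 611 per group (section 14.3).
- Tests two-sided at 0.05 (section 14.4).

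**Assumed**
- c, the probability of change given a major malformation. The protocol gives no value, so a range is shown.
- All between-group contrasts in prevalence.

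**The plan's own figure.** The protocol states none for this endpoint. Its nearest figure reproduces: 0.955 × 0.97 × 0.991 = 0.918, or 8.2% with any of the three outcomes. The observed 97.3% leaves 100 − 97.3 = 2.7% with any of them, so major malformation is at most 2.7%.

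**Step 1: what the whole-set proportion measures.** With m the share of infants with a major malformation, the proportion is m × c and cannot exceed m.
- m = 4.5%: 0.45% at c = 0.1, 1.35% at 0.3, 2.25% at 0.5, 3.60% at 0.8. At least 95.5% of infants are zeros by construction.
- m = 2.7%: 0.27%, 0.81%, 1.35% and 2.16% at the same values.

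**Step 2: between-group ratio.** (m1 × c1)/(m2 × c2) reduces to m1/m2 whenever c1 = c2, whatever the common value.
- Prevalence 4.5% against 3.0%, c = 0.30 in both: 1.35% against 0.90%, ratio 1.5 with no difference in course.
- Same prevalences, c = 0.30 against 0.40: 1.35% against 1.20%, opposite in direction to the difference in course.
- Prevalence 3% against 6%, c = 0.5 in both, Fisher's test enumerated exactly: it rejects in 36% of trials on 611 per group, and in 4% when restricted to malformed infants.

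**Step 3: how much comes from prevalence.** The share of the sampling variance of the log proportion due to prevalence is c(1 − m)/(1 − mc). At m = 4.5%:
- c = 0.2: 0.191/0.991 = 19%
- c = 0.3: 0.2865/0.9865 = 29%
- c = 0.5: 0.4775/0.9775 = 49%
- c = 0.8: 0.764/0.964 = 79%

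The whole-set version still responds to course. With m = 4.5% in both groups and c = 0.25 against 0.50, Fisher's test rejects in 26% on the whole set and in 37% on malformed infants only.

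**Step 4: events for the logistic model**, both groups together at c = 0.30.
- 1,222 × 0.045 × 0.30 = 16.5
- 1,222 × 0.027 × 0.30 = 9.9, an upper limit

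Against these 10 to 16 changes stand 15 listed terms, counting study site and race as one each although both can have several levels.

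**Step 5: base after restriction.**
- 611 × 0.045 = 27.5 per group
- 611 × 0.027 = 16.5 per group, at most

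Missing 1-year information lowers both. A rough 95% half-width at c = 0.30 is 1.96 × √(0.21/27) = 17 percentage points, or 1.96 × √(0.21/16) = 22 points.

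**The case against.** The strongest reply is that nothing in the protocol applies the whole-set denominator to this endpoint specifically. The general sentence cannot be fully literal for 1-year outcomes: the set consists of pregnancies, some ending without a live infant, while this endpoint counts infants. Height and weight at 1 year fall under the same sentence. It may therefore name only a source population, with each endpoint's base nested inside it, and a statistical analysis plan that is not at hand may supply the base. This stands in part. A reader might infer that the protocol firmly sets a wrong denominator; it does not. But the protocol writes a restriction out where it wants one (22 completed weeks for the primary endpoint) and writes none here. It also fixes both the comparison and the model for the 1-year proportions; the deferral to the analysis plan in section 14.4 concerns stepwise adjustment. This is therefore more than detail left for later.

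A reader might also infer that the endpoint mostly re-measures prevalence, or cannot detect a difference in course. Step 3 supports neither: the prevalence share is 29% at a 30% change rate and about half only at 50%, and some power for course remains.

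The contrasts in step 2 are assumptions, and the first is small in counts: 611 × 0.0135 = 8.2 against 611 × 0.009 = 5.5 infants. A ratio of 1.5 on such numbers should not persuade anyone.

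Finally, the restricted proportion has limits too. It conditions on an outcome that arises after exposure, in a non-randomised cohort, and it still pools progression with regression. Both points stand.

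**Conclusion.** The concern holds in this form: a key secondary endpoint has no denominator of its own, and the one population rule the protocol states would make it a product of prevalence and change. It is then confounded with prevalence at birth. The identity in step 2, that a common change rate gives a ratio equal to the prevalence ratio, needs no assumption about that rate. The size of the distortion does, and the protocol gives no figure; across change rates of 0.2 to 0.8 the prevalence share of the variance runs from 19% to 79%.

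The logistic model is unsupportable on either base: about 10 to 16 changes in all, at an assumed 30% change rate and with 1,222 infants followed. The lower figure rests on the observed 97.3% and is a ceiling, since it treats every observed primary event as a major malformation.

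This should be corrected, but it does not touch the primary analysis or the sample size.

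**What to change.** In sections 4.2.2.3 and 14.4, define the denominator as live-born infants with a major malformation recorded by the 1-month follow-up and with 1-year information. Repeat the definition where section 1 lists the endpoint. Report counts and proportions by group with exact confidence intervals, descriptively, and remove this endpoint from the 1-year logistic model in section 14.4.

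The cost is a few sentences. The data are already planned: malformations at delivery (section 8.3.11), those found later at 1 month (section 8.1.4), and changes at 1 year (section 8.1.5). The price is that the small base becomes visible and the intervals are wide. Because the proportion is conditional on a post-exposure outcome, present it next to the section 4.2.2.2 endpoint on live births with major malformations and say that the two must be read together.
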